At visit 4, participants will undergo spirometry to establish corticosteroid responsiveness. Participants will be randomized in a 1:1 allocation to: a) high dose vitamin D (100,000 IU load followed by 4,000 IU/day) plus low dose inhaled corticosteroid (ICS+D), or b) placebo vitamin D-like capsules plus low dose inhaled corticosteroid (ICS). All participants will receive open-label low dose inhaled corticosteroid and double-blind vitamin D capsules. At visit 5 U_{Ca}/U_{Creat} ratios will be monitored for hypervitaminosis D. At subsequent visits 6, 8 and 10, 25(OH)D and U_{Ca}/U_{Creat} ratios will be monitored for hypervitaminosis D (91). Treatment failure criteria will be thoroughly evaluated at each clinic visit, and participants will be asked to contact the clinical site between visits if they experience symptoms of treatment failure. During the treatment phase, the inhaled corticosteroid dose will be held stable for 12 weeks (Phase I), followed by a 50% inhaled corticosteroid reduction for 8 weeks (Phase IIa), and then a 75% inhaled corticosteroid reduction for the final 8 weeks (Phase IIb) (see below). A second methacholine bronchoprovocation will be performed in all participants at visit 6. A second sputum induction will be performed at visit 6 in 200 participants who provided an adequate sputum sample at visit 3. Throughout the treatment phase, participants will be assessed for colds and the WURSS-21 administered when a participant qets a cold. Exit interview will be conducted at visit 10.

B. Corticosteroid taper phases

At visit 6, participants will undergo tapering of their open-label inhaled corticosteroid dose if stability criteria are met (similar to those used in prior ACRN trial (80)). The purpose of corticosteroid tapering is to test the hypothesis that the addition of vitamin D may allow sparing of corticosteroid dose in participants with stable asthma. Furthermore, we will determine if the addition of vitamin D

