5	The purpose of this visit is to assess participant adherence with run-in medications and study
6	procedures and to perform additional study procedures. Eligibility assessment for randomization is
7	made at this visit.
8	Procedures Performed:
9	Review of Participant Adherence with Run-in Medications
10	Asthma Control Test
11	Asthma Symptom Utility Index
12	Asthma Bother Profile
13	Sinonasal Questionnaire
14	Pregnancy Test (in all females of child-bearing potential)
15	Spirometry
16	Methacholine Bronchoprovocation
17	Induced Sputum
18	Vitamin D Dietary Intake Questionnaire
19	Sun Exposure Questionnaire

1 Skin Pigmentatior	n (Melanin)	Measurement
---------------------	-------------	-------------

- 2 Diary and Peak Flow Review
- 3 Eligibility Assessment
- Dispensation of Open-Label Prednisone Supply (for OCS response at visit 4)
- 5 Dispensation of low dose inhaled corticosteroid and single-blind placebo vitamin D
- 6 Blood Draw for DNA Isolation (can be drawn at V3 or V6 as an option)
- 7 Urine Calcium / Creatinine Ratio measurement

Visit 4, Week 5 (-2 day window)

8

9

10

11

12

13

14

15

16

17

18

The purpose of this visit is to assess participant adherence with study procedures, determine the response to the 5 + 2 days of prednisone and to perform study randomization procedures. Participants will be scheduled to return to the clinical site on day 5, 6, or 7 of prednisone in order to provide oral corticosteroid response data. In extenuating circumstances, if a participant cannot return by day 7 of prednisone, allowances will be made for the participant to return for visit 4 within 2 weeks of visit 3. In cases where more than 7 days have elapsed between visit 3 and visit 4, data will not be used for corticosteroid response analyses. If a participant cannot return for visit 4 within 2 weeks of visit 3, he or she will be terminated from the study and can consider re-screening at a later date.

Procedures Performed:

- Review Participant Adherence with study medications and oral prednisone
- 19 Diary and Peak Flow Review
- 20 Cold Questionnaire (WURSS-21) Dispensation and Explanation
- 21 Spirometry for oral corticosteroid response

1	Randomization
2	Dispensation of Randomized Study Drugs (open-label 100% inhaled corticosteroid dose
3	and blinded Vitamin D/placebo)
4	Dispensation of Rescue Prednisone
5	Telephone contact, Week 8
6	Review participant's use of Study Medications, Answer Questions, and Assess for

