7	Treatment Failures (participant will be scheduled for treatment failure visit, if appropriate)
8	Visit 5, Week 11 (-5/+5 day window)
9	Continuing treatment with 100% inhaled corticosteroid dose and Vitamin D / placebo.
10	Procedures Performed:
11	Asthma Control Test
12	Asthma Symptom Utility Index
13	Review of Participant Adherence with Study Medications
14	Diary, Cold Questionnaire and Peak Flow Review
15	Spirometry
16	Treatment Failure Assessment
17	Urine calcium/creatinine ratio measurement
18	Telephone contact, Week 14
19	Review participant's use of Study Medications, Answer Questions, and Assess for
20	Treatment Failures (participant will be scheduled for treatment failure visit, if appropriate)

2	Visit 6,	Week 17	(-5/ +5 da	y window)

3	End treatment with 100% inhaled corticosteroid dose and Vitamin D/placebo.	
4	Procedures Performed:	
5	Asthma Control Test	
6	Asthma Symptom Utility Index	
7	Sinonasal Questionnaire	
8	Review of participant adherence with Study Medications	
9	Diary, Cold Questionnaire and Peak Flow Review	
10	Physical Exam (short)	
11	Spirometry	
12	Treatment Failure Assessment	
13	Methacholine Bronchoprovocation	
14	Urine Pregnancy Test (if female of child-bearing potential and undergoing methacholine	
15	bronchoprovocation)	
16	Induced Sputum	
17	Serum 25 (OH) D measurement	

Urine calcium/creatinine ratio measurement

1	Dispensation of Randomized Study Drugs (open-label 50% inhaled corticosteroid dose and
2	blinded vitamin D/placebo)
3	Visit 7, Week 21 (-5/+5 day window)
4	Continuing treatment with 50% inhaled corticosteroid dose and Vitamin D/placebo
5	Procedures Performed:
6	Asthma Control Test
7	Asthma Symptom Utility Index
8	Review of participant adherence with Study Medications
9	Diary, Cold Questionnaire and Peak Flow Review
LO	Spirometry
l1	Treatment Failure Assessment
12	Dispensation of Randomized Study Drugs
L3	Visit 8, Week 25 (-5/+5 day window)
L4	End treatment with 50% inhaled corticosteroid dose and Vitamin D/placebo.
L5	Procedures Performed:
L6	Asthma Control Test
L7	Asthma Symptom Utility Index
L8	Review of Participant Adherence with Study Medications
L9	Physical examination (short)

1	Diary, Cold Questionnaire and Peak Flow Review
2	Spirometry
3	Treatment Failure Assessment
4	Serum 25 (OH) D measurement
5	Urine calcium/creatinine ratio measurement
6	Dispensation of Randomized Study Drugs (open-label 25% inhaled corticosteroid dose and
7	blinded Vitamin D/placebo)

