8	Visit 9, Week 29 (-5/+5 day window)
9	Continuing treatment with 25% inhaled corticosteroid dose and Vitamin D/placebo.
10	Procedures Performed:
11	Asthma Control Test
12	Asthma Symptom Utility Index
13	Review of Participant Adherence with Study Medications
14	Diary, Cold Questionnaire and Peak Flow Review
15	Spirometry
16	Treatment Failure Assessment
17	Dispensation of Randomized Study Drugs
18	Visit 10, Week 33 (-5/+5 day window)
19	This visit will conclude the study.

1	End treatment with 25% innaled corticosteroid dose and Vitamin D/placebo.
2	Procedures Performed:
3	Height, weight; waist, hip, neck (anthropometrics)
4	Physical examination (long)
5	Asthma Control Test
6	Asthma Symptom Utility Index
7	Asthma-specific Work Productivity and Activities Impairment Questionnaire
8	Asthma Bother Profile
9	Perceived Stress Scale
10	Review of Participant Adherence with Study Medication
11	Diary, Cold Questionnaire and Peak Flow Review
12	Urine Pregnancy Test (for all women of child-bearing potential)
13	Spirometry
14	Treatment Failure Assessment
15	Serum 25 (OH) D Measurement
16	Urine calcium/creatinine ratio measurement
17	Vitamin D Dietary Intake Questionnaire
18	Sun Exposure Questionnaire

1	Skin Pigmentation (Melanin) Measurement
2	AsthmaNet Satisfaction Questionnaire
3	Exit Interview
4	Exit visit (in those participants who have been randomized and are withdrawing consent or meet drop-
5	out criteria (i.e., more than two treatment failures))
6	Asthma Control Test
7	Review of Participant Adherence with Study Medication
8	Diary, Cold Questionnaire and Peak Flow Review
9	Spirometry
10	Treatment Failure Assessment
11	Serum 25 (OH) D Measurement
12	Exit Interview
13	Treatment failure or Exacerbation Visit
14	This visit will be performed if a participant experiences treatment failure or exacerbation conditions
15	between regularly-scheduled study visits and needs to be seen at the clinical site. Procedures to be
16	performed include:
17	Physical Examination (long)
18	Asthma Control Test
19	Review of Participant Adherence with Study Medication

- Diary, Cold Questionnaire and Peak Flow Review
- 2 Spirometry
- 3 Treatment Failure Assessment

D. Study Procedures

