Pulmonary Function Testing. All participants will undergo spirometry at visits 1 and 3-10. Spirometric studies are performed in accordance with ATS recommendations (92) and AsthmaNet manuals of procedure (MOP). All participants will undergo methacholine bronchoprovocation at visits 3 and 6 [and visit 2 if no evidence of bronchodilator responsiveness at visit 1] in accordance with ATS recommendations (93) and AsthmaNet MOP. A positive response is considered a drop in the FEV₁ from post-diluent FEV₁ ≥20%.

Corticosteroid-responsiveness phenotype. Many patients with moderate to severe asthma (with bronchial hyperresponsiveness) do not demonstrate corticosteroid reversibility likely due to airway remodeling (6, 94). All participants will be characterized as corticosteroid responsive or nonresponsive based on reversibility of airflow obstruction at visit 4 following systemic corticosteroid provided at visit 3. Corticosteroid-responsive airflow obstruction will be defined as a ≥5% improvement in FEV₁ after the administration of 5 + 2 days of prednisone 40 mg/day measured at visit 4 compared to the baseline value at visit 3. If the participant's FEV₁ does not improve by at least 5%, they will be considered to have corticosteroid-nonresponsive airflow obstruction. We have chosen to define the corticosteroid responsive phenotype at visit 3 so that all participants will have completed 4 weeks of run-in medication (confirmed by adherence monitoring). Furthermore, we have used a cut-off of 5% change in FEV₁ based on our experience with systemic corticosteroid response (18). However, we will perform additional subset analysis using the median split, 7.5% and 10% change in FEV₁ as alternate

cutoffs [as they have been used to define inhaled corticosteroid response (17, 19)], as well as the proportion of participants who achieve normal lung function as defined by an FEV₁ ≥85% predicted.

Bronchodilator reversibility phenotype. Participants will undergo spirometry with bronchodilator reversibility testing and maximal bronchodilation as defined by the maximal achievable FEV₁ after levalbuterol (up to 360 mcg or 8 puffs). Participants will withhold medications as per the AsthmaNet MOP. Bronchodilator reversibility has been shown to predict subsequent inhaled corticosteroid response (17-19) and will be evaluated as a covariate potentially influencing the primary endpoint.

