- 5 will be used to determine if the participants meet the inclusion criteria for this study. Spirometry
- 6 will be used during the study to monitor for treatment failure.
- 7 The potential benefits justify the potential risks.
- 8 Methacholine inhalation challenge: Methacholine challenge will be used to assess airway hyper-
- 9 responsiveness.
- 10 Risks: The major risk of methacholine challenge is the induction of severe bronchoconstriction.
- As a precaution, participants will not undergo methacholine challenge if their FEV₁ is less than
- 12 55% of predicted or 1.0 liter. Medical and nursing personnel, medications and equipment will be
- available at the study sites to treat and manage any bronchoconstriction episodes.
- 14 Benefits: There are two benefits to this procedure. First, for the participants who do not
- demonstrate a 12% improvement in FEV₁, a positive methacholine challenge would allow them to
- meet one of the inclusion criteria for this study. Second, the comparison of the baseline and end
- of treatment methacholine challenge results will allow for an assessment of the effect of study
- drug treatment on airway hyperresponsiveness.
- 19 The potential benefits justify the potential risks.
- 20 Induced sputum: Sputum will be induced with hypertonic saline to collect an airway sample and to
- 21 assess for airway inflammation.
- 22 Risks: Like any bronchoprovocation challenge, sputum induction can provoke bronchospasm and

- warrants close supervision during its performance.
- 2 Benefits: There are no direct benefits to the participant. This procedure will allow us to assess for
- the effect of vitamin D on airway inflammation and potential biologic mediators of vitamin D's
- 4 effect, such as increasing cathelicidin levels in the airway.
- 5 The potential benefits justify the potential risks.
- 6 Allergy skin testing: Epicutaneous (prick skin) testing will be used to determine IgE sensitivity to
- 7 areoallergens.
- 8 Risks: Possible risks include itching at the site of the skin tests, and systemic allergic reaction to
- 9 the allergens tested. The allergic reactions range from mild (urticaria) to moderate (wheezing) to
- severe (upper airway angioedema, anaphylaxis). Medical and nursing personnel, medications
- and equipment will be available at the study sites to treat and manage any allergic reactions.
- Benefits: Allergy skin testing results will be used to determine if there is a difference in response

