26		If Yes, how often?	□₁ At lea	ast once a week										
27			□₂ Less t	than once a week, but at	t least once a month									
28			□₃ Less t	than once a month, but r	more than two times a	year								
29			□₄ Less	than or equal to two time	es a year									
30														

D. Appendix D. Melanin Recording

SmartProbe 400 "L" measurements from four body areas. "L" is a measure of lightness or darkness (0=black, 100=white).

Body Area	First L Reading	Second L Reading				
Upper Inner Arm	0-100	0-100				
Outer Forearm	0-100	0-100				
Exposed Forehead	0-100	0-100				
Abdomen/Stomach	0-100	0-100				

E. Appendix E. Protocol Table.

Visit	0	1	2	3	4	5	6	7	8	9	10	TF***
Week	Pre- Scr	Scr	0	4	5	11	17	21	25	29	33	
Window (regular/extended)(Days)				+3/+7	-2/+7	±3/ ±5	±3/ ±5	±3/ ±5	±3/ ±5	±3/ ±5	±3/ ±5	
Randomization					Χ							
Steroid inhaler dose taper (if stable)							Χ		Χ			
Informed consent	Х											
Brief medical history	Χ											
Full medical history		Χ										
Long physical exam		Х									Χ	Χ
Short physical exam							Χ		Χ			
Height/weight/BMI		Х									Χ	
Body measurements (waist, hip, neck)		Х									Χ	
Melanin test				X							Χ	
Allergy skin testing ⁺⁺			Х									
Genetics blood sample				Х								
Serum vitamin D	Х						Х		Χ		Χ	
Serum calcium		Х										
Serum creatinine/eGFR		Х										
Urine calcium and creatinine ratio		Х		Х		Х	Χ		Χ		Χ	
Urine pregnancy test			X	Х			Х				Χ	
Spirometry		Х	X	Х	Х	Х	Х	Х	Χ	Х	Χ	Х
Maximum bronchodilator reversal		Х										
Methacholine challenge			X	X			Χ					
Sputum induction				Х			X ⁺					
Cold questionnaire (WURSS-21)					\ \ \ \ \ \ \ \ \ \ \ \ \ \ \ \ \ \ \							
distribution/instruction					X							
Asthma Control Test (ACT)		Х		Х		Х	Х	Х	Χ	Х	Χ	Х
Asthma Bother Profile (QOL) (ABP)		Х		X							Χ	
Asthma Symptom Utility Index (ASUI)		Х		X		Х	Χ	Χ	Χ	Χ	Χ	
Asthma-Specific Work Productivity and								İ				
Activities Impairment Questionnaire			X								Χ	
(WPAI:Asthma)												
Home Environment Questionnaire (HEQ)		Х										
Household Socio-Economic Information		Х										
questionnaire (HOUSEHOLD_SEI)		^										1
Perceived Stress Scale (PSS)			Х								Χ	

Visit	0	1	2	3	4	5	6	7	8	9	10	TF***
Week	Pre- Scr	Scr	0	4	5	11	17	21	25	29	33	
Window (regular/extended)(Days)				+3/+7	-2/+7	±3/ ±5	±3/ ±5	±3/ ±5	±3/ ±5	±3/ ±5	±3/ ±5	
Sinonasal Questionnaire (SNQ)				Х			Χ					
Sun Exposure Questionnaire (SEQ)				Х							Χ	
Vitamin D Intake Questionnaire				Х							Χ	
Review diaries				Х	Х	Х	Χ	Х	Χ	Х	Χ	Х

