Review medication use				Х	Х	Х	Χ	Х	Χ	Х	Χ	
Satisfaction questionnaire											Χ	
Prednisone burst				Х								
Treatment failure assessment				Х	Х	Х	Χ	Х	Χ	Х	Χ	Х
Dispense e-diary/PEF meter			Х									
Dispense run-in medications (open-label ICS and single-blind vit D capsules)			Х	Х								
Dispense rescue prednisone supply					Х							
Dispense randomized medications (open-label ICS and double-blind vit D capsules)					Х	Х	Х	Х	Х	Х		

At visit 2, participants who did not show adequate bronchodilator reversal at visit 1 will complete spirometry, a urine pregnancy test (for women of child-bearing potential), and a methacholine challenge test.

^{**} The genetics blood sample may be postponed until the time of the vitamin D blood test at visit 6.

^{***} Additional visits to the clinical site will be required if the participant experiences treatment failure conditions between regular study visits.

⁺ Approximately 200 people will undergo sputum induction at visit 6. Only those whose sputum sample at visit 3 was deemed adequate through lab analysis will be eligible to have the sputum induction at visit 6.

⁺⁺ If washouts required for skin testing at visit 2 are not met, the skin test may be deferred to a future visit.

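### Section VI.C ties the Visit 6 pregnancy test to the methacholine challenge, so a woman barred from the challenge for low FEV1 has no scheduled test while on blinded capsules

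*Protocol*

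**What the plan says.** The protocol schedules pregnancy tests in VI.C (Detailed visit structure) and in the Appendix E table.

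- **Visit 3, week 4 (VI.C):** "Pregnancy Test (in all females of child-bearing potential"), whether or not a challenge is done.
- **Visit 6, week 17 (VI.C):** "Urine Pregnancy Test (if female of child-bearing potential and undergoing methacholine" bronchoprovocation). Two conditions must both hold.
- **Visit 10, week 33 (VI.C):** "Urine Pregnancy Test (for all women of child-bearing potential"), again with no link to a challenge.
- **All other post-randomization contacts (VI.C):** no pregnancy test is listed at Visits 4, 5, 7, 8 or 9, at the exit visit, or at the treatment failure visit.
- **Appendix E:** the row "Urine pregnancy test" is marked at Visits 2, 3, 6 and 10. The one surviving note that conditions a pregnancy test concerns Visit 2: "At visit 2, participants who did not show adequate bronchodilator reversal at visit 1 will complete spirometry, a urine pregnancy test" and a challenge.

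The challenge itself is planned for everyone. VI.A states: "A second methacholine bronchoprovocation will be performed in all participants at visit 6". VI.D states: "All participants will undergo methacholine bronchoprovocation at visits 3 and 6". IX.A sets the safety limit: "participants will not undergo methacholine challenge" if FEV1 is under 55% of predicted or 1.0 L. Entry criterion 5 in V.A requires FEV1 of at least 50% of predicted and gives no limit in litres. X.F makes pregnancy a ground for drop-out, with all study medications stopped.

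**The concern.** At Visit 6 a participant is on blinded vitamin D or placebo with more than half of the treatment period still to come. This is the one scheduled point at which a pregnancy test could lead to stopping the capsules as X.F provides. Visit 3 precedes randomization, and Visit 10 is the end of dosing.

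VI.C makes that test depend on a lung-function procedure. A woman whose FEV1 is too low for the challenge is as likely to be pregnant as any other, yet VI.C drops her test. The entry floor and the challenge floor do not coincide, so an eligible participant can fall into this position. VI.C and Appendix E could also be followed differently by two sites acting in good faith. The stake is a small gap in on-treatment safety monitoring. Nothing in the primary or secondary analyses depends on it.

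**Working it through.** The protocol gives no figure of its own for this point. The check compares the sections and subtracts nominal study weeks, ignoring visit windows.

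**1. Can an eligible woman fail the methacholine condition?**
- Entry floor: FEV1 at least 50% of predicted (V.A, criterion 5). Challenge floor: 55% of predicted or 1.0 L (IX.A). The range from 50% to below 55% is eligible but barred, as is an FEV1 below 1.0 L that still meets the percentage criterion.
- She does not need a challenge at Visit 2 to enter. Criterion 3 accepts bronchodilator reversibility of at least 12% at Visit 1, or documentation of a qualifying AsthmaNet challenge within 6 months of Visit 2.
- The randomization criteria in V.C do not require a completed Visit 3 challenge.

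So a woman with FEV1 steady at 50 to <55% of predicted can be randomized. She is tested at Visit 3 but, under VI.C, not at Visit 6.

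**2. Can a woman fall below the limit later without being an FEV1 treatment failure?**
The FEV1 failure threshold is 80% of the Visit 3 value (III.C). Staying above it while dropping below the challenge floor requires a Visit 3 value under:
- 55 / 0.80 = 68.75% of predicted, or
- 1.0 / 0.80 = 1.25 L.

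Example: with a Visit 3 value of 65% of predicted, 0.80 × 65 = 52%. A Visit 6 value above 52% and below 55% means no challenge and no FEV1 treatment failure.

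**3. What if FEV1 is at or below 80% of Visit 3 at Visit 6?**
III.C withholds provocative procedures that day and calls for repeat spirometry in 24 to 96 hours. If FEV1 recovers, all the visit's procedures are done, including the challenge and hence the test. If it does not, the participant is a treatment failure, and the protocol does not say whether the challenge is done later. Omission of the test by this route is possible but not stated.

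**4. Length of the gap**
- VI.C, no test at Visit 6: 33 − 4 = 29 weeks.
- With a test at Visit 6: 17 − 4 = 13 weeks, then 33 − 17 = 16 weeks.

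The 29 weeks cover the whole randomized period (33 − 5 = 28 weeks).

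**5. Dosing that a Visit 6 test could still affect**
- Daily capsules from week 17 to week 33: 16 × 7 = 112.
- In the vitamin D arm, with full adherence: 112 × 4,000 IU = 448,000 IU.

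The 100,000 IU load follows randomization at Visit 4, about one week after the unconditional Visit 3 test. A Visit 6 test cannot affect it.

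**The case against.** The strongest defence is that VI.C is coherent as written. Visits 2 and 6 tie the test to the challenge and can be read as pre-challenge checks. Visit 3, before prednisone and randomization, and the closing Visit 10 test all women of child-bearing potential. The protocol sets no interval for pregnancy testing on treatment, so a 29-week gap breaks no stated rule. As planned, everyone is challenged at Visit 6, so nobody is missed.

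Much of this stands. It does not settle the point, because IX.A overrides the plan to challenge everyone, and the woman it excludes is then untested for a reason that concerns her lungs only. The comparison with Visit 2 is also incomplete: at Visit 2 only inhaled corticosteroid and placebo capsules are dispensed, whereas at Visit 6 she may be taking active drug.

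The affected group is narrow. A woman already below the limit at Visit 2 must have qualified by reversibility or an earlier challenge, and she must still be below it after months on study inhaled corticosteroid.

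A reader might infer that Appendix E contradicts VI.C by requiring an unconditional Visit 6 test. The documents do not support that. The table's marks are shorthand: they do not mention child-bearing potential either, and the Visit 2 mark in the same row is conditional. Methacholine is also marked at Visit 6, and footnote markers were lost in the text as read. The absence of a surviving condition is weak evidence, so it is inference to say that a site using the table would test these women.

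**Conclusion.** The point holds as a minor one. Under VI.C an eligible woman who is below the challenge limit at Visit 6 has no scheduled pregnancy test for 29 weeks, spanning all of her blinded dosing, where 13 and 16 weeks were available. Between VI.C and Appendix E there is an ambiguity only.

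The conclusion assumes that sites apply the IX.A limit and follow the VI.C list literally. The number of women affected cannot be derived from the protocol and is probably small.

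A reader might also infer a substantial fetal risk from the cumulative dose. The protocol gives no basis for that: it states no fetal hazard at the study dose, and VII.B cites an ongoing maternal supplementation study at the same 4,000 IU/day. The 448,000 IU is a maximum for one arm and is tied to no stated harm. Contraception is required for the whole study (V.A, criterion 10), and drop-out for pregnancy under X.F does not need a scheduled test to trigger it. The safety gain from testing is therefore modest. Sample size, power and all analyses are unaffected.

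**What to change.** In VI.C, Visit 6, delete the part of the condition that refers to undergoing the methacholine challenge, so that the test applies to all women of child-bearing potential, as at Visits 3 and 10. This also removes the ambiguity with the Visit 6 mark in Appendix E.

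The cost is one clause and a few extra pregnancy tests. Urine is already collected at Visit 6 for the calcium/creatinine ratio, so no additional sample is needed.
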